- We believe that this study will generate an estimate of the effect that can be used to inform the development of randomized controlled studies (RCTs).
 - This study will also generate RCTs examining the use of the Oculus VR as a form of stroke rehabilitation that is scalable to the participant's home setting.
 - There are few studies that have examined the role of caregiver engagement on the success of remote stroke rehabilitation.
- The caregiver will be encouraged to use Caregiver Cues (Appendix D) as this will help the caregiver to engage with the participant using encouragement or positive cues to the stroke participants to support them during the session.
- The therapist or RA (who will be trained by the therapist) who is conducting the session will use the Therapist Guided Cues (Appendix E) to guide the stroke participant with problem solving and planning for performing home exercises that will be provided to the participant at the first session.
- The data we obtain from caregivers and stroke survivors (dyads) will inform future studies that examine ways to best support the dyads to improve stroke rehabilitation outcomes and reduce stress in the caregivers. (See Appendix F)

Statistical Analysis

- To address S.A.1., feasibility, usability, and acceptability of the Oculus VR headsets for upper extremity and cognitive therapies will be analyzed as follows: Feasibility: Assessed from the number sessions attended and time spent using the Oculus VR. The minimum number of sessions expected for a user are 2 per week (8 sessions) and the minimum time spent playing Job Simulator is 1 hour per week (4 hours) through the end of the study. Descriptive statistics of the participation rates and measures including frequencies, median and interquartile ranges for sessions attended and time spent using the game. Usability: Descriptive statistics for demographic and clinical data and participant scores on the SUS and PQ will be calculated. (See Appendix G and H) We will refrain from using inferential statistics since this is a pilot study and hypothesis testing is not the objective. Acceptability: Descriptive statistics for scores on the SSQ will be calculated at baseline and after each session (See Appendix I). We will examine the trend of symptoms for each participant.)

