- To address S.A.2. As part of standard of care, we will calculate change in arm and cognitive scores for each stroke participant from the following tests: MoCA, FM, and ARAT. (See Appendix J, K, and L) After inspection of the distribution, either the paired t-test or the nonparametric Wilcoxon signed rank test will be used to evaluate the significance of the difference score. However, statistical inference is not the primary interest of this pilot study. The effect size provided by Cohen's d measure, i.e., the standardized difference of mean score, will provide a preliminary measure of the effectiveness of Oculus VR in this pilot study. Similarly, standardized differences in the BSFC-s scores will provide the effect sizes for the change in caregiver burden.
- To address S.A.3., interview data will be analyzed following methods for thematic analysis.^{34,35} Using a qualitative data analysis program, Atlas.ti,³⁶ 2 researchers will review transcripts to gain a sense of the whole, identify codes, categories, and generate higher order themes to describe

the role of caregiver engagement during the session. Reasons for non-participation will be obtained from those eligible participants who decline participation. Unacceptable components and reasons for non-participation will be considered in the planning and designing of future trials.

Outcomes

- Upon completion of these aims, the expected outcomes are to develop randomized control trials (RCTs) to determine the effectiveness of the Oculus VR for stroke rehabilitation. We anticipate using the information from the dyadic interviews to develop qualitative studies and RCTs examining the role of the caregiver on remote stroke rehabilitation outcomes.
- Please see Table 1 (below) for the outcomes with timepoints.

Primary and Secondary Outcomes with Timepoints			
Primary	Timepoint	Secondary	Timepoint
MoCA (Appendix J)	Baseline and Last Session	Pre-Intervention Questionnaire (Appendix R)	Baseline Session
Fugl-Meyer (Appendix K)	Baseline and Last Session	Therapy Follow-Up Checklist (Appendix M)	Session 2 – Last Session
ARAT (Appendix L)	Baseline and Last Session	Post-Intervention Questionnaire (Appendix S)	Last Session
Caregiver Burden Scale (for caregiver only; Appendix F)	Baseline and Last Session		
Simulator Sickness Questionnaire (Appendix I)	Session 1 – Last Session		
System Usability Scale (Appendix G)	Last Session		
Presence Questionnaire (Appendix H)	Last Session		

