Appendix A
Description of Instruments

Variables	Specific Aims	Stroke Participants	Informal Caregiver	Data Collection Procedures
		Measures/Descriptions	Measures/Descriptions	
Pre-Intervention Questionnaire (Appendix R; Secondary Outcome)		Demographic data will be collected via survey (e.g., age, sex, race, education, health history, prior technology use, etc.)	Demographic data will be collected via survey (age, sex, race, education)	Baseline (RedCap), The PI, therapist, and/ or RA will review the data with the participants)
Feasibility (Primary Outcome)	SA1	Number of sessions attended; Duration (minutes) of session	N/A	Continuous – PI, therapist, and/ or RA will maintain log
Usability (Appendix G; Primary Outcome)	SA1	The System Usability Scale (SUS) ¹ measures the impact, perceived usefulness and ease of use, and user control of the technology using a 5- point Likert scale (1= strongly agree to 5= strongly disagree) with a score range 0-100. Higher scores (>68) indicate higher perceived usability. The SUS is a widely-used 10-item validated instrument with a Cronbach's alpha of .91. ²	N/A	Post-intervention (RedCap)

Variables	Specific Aims	Stroke Participants	Informal Caregiver	Data Collection Procedures
		Measures/Descriptions	Measures/Descriptions	
Usability (Appendix H; Primary Outcome)	SA1	The Presence Questionnaire (PQ ver.3) evaluates the user's level of presence in the VR environment on a 7-point scale with 1 being the lowest and 7 the highest level of presence. The PQ is widely-used in VR research is a validated instrument with a Cronbach's alpha of .91. ³		of 87% in detecting mild cognitive impairment ⁶ .
Acceptability (Appendix I; Primary Outcome)	SA1	The Simulator Sickness Questionnaire (SSQ) ⁴ is comprised of 16 items that capture physical symptoms commonly associated with prolonged activity in a simulator. Each symptom is ranked in order of effect on the user (none, slight, moderate, severe.). The SUS is widely-used in VR research is a validated instrument with a Cronbach's alpha ranging from .84-.94 on subdimensions. ⁵		

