Cognitive Assessment (Appendix J; Primary Outcome)	SA2	The Montreal Cognitive Assessment (MOCA) is a 30-item screening tool used to detect cognitive impairment that takes 10 minutes to complete. It measures cognition measures including attention and memory. The MOCA has good evidence of internal consistency (Cronbach's alpha = .82) and test-retest reliability (r = .92) ⁶ . At a cutoff score of 26, MOCA has a sensitivity of 90% and specificity		

N/A

P
o
s
t
-
i
n
t
e
r
N/A
e
n
t
i
o
n
(
R
e
d
C
a
p
)

nuous – the participant
will be evaluated with the
SSQ by PI, therapist, or
RA before and after the
intervention

Baseline & Post-
Intervention - the PI,
therapist or RA will
conduct the cognitive
evaluation

N/A

C
o
n
t
i

Variables	Specific Aims	Stroke Participants	Informal Caregiver	Data Collection Procedures
		Measures/Descriptions	Measures/Descriptions	
Upper Limb Assessment (Appendix K; Primary Outcome)	SA2	The Fugl-Meyer Assessment-Upper Extremity ⁷ is scored on 7 domains on a 3-point scale (0 - cannot perform, 1 -performs partially, 2 - performs fully) for a total of 66 points. It is a validated instrument with a Cronbach's alpha of .88-.90. ⁸	N/A	Baseline & Post intervention – the occupational therapist and/ or RA will conduct the upper extremity assessment
Upper Limb Assessment (Fine motor) (Appendix L; Primary Outcome)	SA2	The Action Research Arm Test (ARAT) has 19 items with 4 subscales (grasp, grip, pinch, and gross movement) and arranged in order of decreasing difficulty. Scoring is recorded on a 4-point scale (0 – no movement, 1 – movement is partially performed, 2 – completed task but abnormally long amount of time, 3 – movement is normal) for a total of 57 points. It is a validated instrument Cronbach's alpha of .98. ^{9,10}	N/A	Baseline & Post intervention – the occupational therapist and/ or RA will conduct the upper extremity assessment
Caregiver Burden (Appendix F; Primary Outcome)	SA3	N/A	The Burden Scale for Family Caregivers (BSFC-s) is a 10-item questionnaire using a 4- point Likert scale (1= strongly agree to 4= strongly disagree). BSFC-s has a Cronbach's alpha of .92 and adequate evidence of convergent and discriminant validity (Giessen Symptom Complaints List-24: r = 0.68; Caregiver Strain Index: r =	

0
.7
0
;
B
e
r
l
i
n
n
v
e
n
t
o
r
y
o
f
C
a
r
e
g
i
v
e
r
s
,

B
u
r
d
e
n
w
i

th Dementia Patients: $r = 0.16$; $p < 0.001$) for

Baseline & Post- Intervention (RedCaep)

n

1

1

.

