
 • Stroke survivors will be excluded if they do not have score ranges that indicate mild to moderate severity on prior post-stroke neuropsychological tests, or the MoCA (15-25) using normative data based on education, age, and other standard demographic data, or other appropriate cognitive screening test selected by the speech language pathologist (also on this application) if the participant has aphasia, hemiopsia, other neurological or specific cognitive deficits, or demographic factors (e.g., education level) that prevents the participant from being accurately examined using MoCA or a modified MoCA; if cognition is within normal range then a FM (20-50) • Have a history of: 
 ◦ Motion sickness ◦ Vertigo ◦ Dizziness ◦ Seizures (a doctor's note will be requested for participants who do not believe their seizures will be triggered by the VR) ◦ Claustrophobia ◦ Blind/deaf • Cannot hold the controller in their affected arm. 	

	IRB NUM: ER: HSC-SN-22-08 8
	IRB APPROVAL DATE: 03/06/2024

1st Session (Week 1)	Initial & Date completed

3. Pre-Intervention Questionnaire will be given during the first session. (Appendix R)
 
4. Cognition (MoCA or other appropriate) test completed (if not completed during pre-first visit) (Appendix J)
 
5. Fugl-Meyer Upper Extremity Assessment (Appendix K)
 
6. Action Research Arm Test (ARAT) (Appendix L)
 
a. 3,4, and 5 will be completed as a part of standard of care.
 
7. Burden Scale for Family Caregivers – short version will be given to the caregivers of the stroke subjects via REDCap. (Appendix F)
	
 Recruit from stroke units/clinics	
 Study coordinator screens for eligibility requirements	
 Obtain Informed Consent Documents from Dyads	
 Complete the Cognition (MoCA) test (pre-intervention) (Primary Outcome; Appendix J)	
 Complete the Fugl-Meyer Upper Extremity Assessment (pre-intervention) (Primary Outcome; Appendix K)	
 Complete the Action Research Atm Test (ARAT) (pre-intervention) (Primary Outcome; Appendix L)	
 Have the Caregivers complete the Burden Scale for Family Caregivers (Primary Outcome; Appendix F)	

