 Arrange sessions schedules with Dyads for the length of the study (2 sessions/week each being an hour minimum in length). Reserve smart room for duration of study.	

 _ Complete the Pre-Intervention Questionnaire (Secondary Outcome; Appendix R) 	

 _ Have the stroke survivor complete the Simulator Sickness Questionnaire (SSQ) at the beginning and end of the first 1-hour session (Primary Outcome; Appendix I) 	
2nd Session (Week 1)	Initial & Date completed

 _ Research Assistant complete the Therapy Follow Up Checklist with Subject before the start of the session. (Secondary Outcome; Appendix M) 	

 _ Have the stroke survivor complete the Simulator Sickness Questionnaire (SSQ) at the beginning and end of the second 1-hour session (Primary Outcome; Appendix I) 	
3rd Session (Week 1)	Initial & Date completed

 Research Assistant complete the Therapy Follow Up Checklist with Subject before the start of the session. (Secondary Outcome; Appendix M) 	

 Have the stroke survivor complete the Simulator Sickness Questionnaire (SSQ) at the beginning and end of the third 1-hour session (Primary Outcome; Appendix I) 	
4th Session (Week 2)	Initial & Date completed

 Research Assistant complete the Therapy Follow Up Checklist with Subject before the start of the session. (Secondary Outcome; Appendix M) 	

 Have the stroke survivor complete the Simulator Sickness Questionnaire (SSQ) at the beginning and end of the fourth 1-hour session (Primary Outcome; Appendix I) 	
5th Session (Week 2)	Initial & Date completed

 Research Assistant complete the Therapy Follow Up Checklist with Subject before the start of the session. (Secondary Outcome; Appendix M) 	

 Have the stroke survivor complete the Simulator Sickness Questionnaire (SSQ) at the beginning and end of the fifth 1-hour session (Primary Outcome; Appendix I) 	
6th Session (Week 2)	Initial & Date completed

 Research Assistant complete the Therapy Follow Up Checklist with Subject before the start of the session. (Secondary Outcome; Appendix M) 	

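### The primary acceptability measure is scheduled before and after every session, but its analysis specifies no within-session change

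*Combined protocol and SAP*

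**What the plan says.** **Collection.** Appendix Q gives the same instruction for every session from the 1st to the 12th; for the 2nd it reads "Have the stroke survivor complete the Simulator Sickness Questionnaire (SSQ) at the beginning and end of the second 1-hour session". In Appendix A the SSQ is the one instrument labelled Acceptability and is marked as a primary outcome. Its collection entry has the investigator, therapist or "RA before and after the" intervention administer it, and its response scale is described as "Each symptom is ranked in order of effect on the user (none, slight, moderate, severe".

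**Analysis.** The S.A.1 paragraph of the Statistical Analysis section gives two statements on the SSQ: "Descriptive statistics for scores on the SSQ will be calculated at baseline and after each session" and "We will examine the trend of symptoms for each participant". It does not say which scores make up the trend, and it does not mention a start-to-end difference.

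**Elsewhere.** Under S.A.2 the plan does specify change for other measures: "we will calculate change in arm and cognitive scores for each stroke participant", from the MoCA, Fugl-Meyer and ARAT, with standardised differences for caregiver burden. In Table 1 the row for the "Simulator Sickness Questionnaire (Appendix I") runs from Session 1 to the last session, with no separate baseline entry.

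**The concern.** The design collects what is needed to see what happens to symptoms during a session: a score on arrival and a score on leaving. The analysis as written does not put the two together.

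This matters because several SSQ items in Appendix I are not specific to a headset. Fatigue, headache, blurred vision and difficulty concentrating may already be present when a chronic stroke survivor arrives. Cognitive impairment is one route into the study. Appendix M also records outside occupational, physical and speech therapy between visits, so the state on arrival may differ from one session to the next. A post-session score of moderate fatigue could mean that the session produced it, left it unchanged or relieved it.

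At stake is how the acceptability result can be read. The text before the References says that acceptability data are needed to show the technology suits home use after stroke. A summary that cannot tell arrival symptoms from symptoms arising in the session is weaker support for that than the scheduled data allow.

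**Working it through.** The plan states no sample size, power or threshold figure for the SSQ, so there is none to reproduce. The check is a comparison of sections, a count and one identity.

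**Inputs**
- Sessions listed: 12, three a week for four weeks (Appendix Q).
- Minimum sessions expected: 8 (Statistical Analysis, S.A.1).
- SSQ administrations per session: 2, start and end (Appendix Q).
- Stroke survivors: 20 (Recruitment).

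**Step 1. Pairs scheduled.** Each attended session yields one start/end pair.
- All 12 sessions: 12 pairs per survivor; 20 × 12 = 240.
- At the minimum of 8: 8 pairs per survivor; 20 × 8 = 160.

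Both totals assume that all 20 survivors attend that number of sessions and complete both forms. No end-minus-beginning summary is specified for any pair.

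**Step 2. What baseline means here.** The contact headed baseline in Appendix Q is the consent contact, and no SSQ is listed there or at the pre-first visit. That does not leave the term open. Table 1 gives Fugl-Meyer and ARAT a baseline timepoint, yet Appendix Q schedules their pre-intervention assessment only under the 1st Session ("Complete the Fugl-Meyer Upper Extremity Assessment (pre-intervention) (Primary Outcome; Appendix K"). Table 1 also puts the pre-intervention questionnaire at the baseline session, and Appendix Q gives it during the first session. Baseline therefore most naturally means session 1 before the intervention, and for the SSQ that is the form completed at the start of session 1. This is inference, but it follows the plan's own usage.

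**Step 3. What a later score against that baseline measures.** For any numeric scoring, and session s:

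post(s) − pre(1) = [post(s) − pre(s)] + [pre(s) − pre(1)]

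The first bracket is change during session s. The second is change in arrival symptoms since session 1, which is zero by definition only when s = 1. For a hypothetical survivor, code none as 0 and moderate as 2 (an assumed coding). Fatigue is none at the start of session 1 and moderate at both the start and the end of session 5. Then post(5) − pre(1) = 2 − 0 = 2, made up of (2 − 2) + (2 − 0) = 0 + 2. The comparison with baseline shows a rise of two categories, although nothing changed during the session. Taken alone, post(5) also cannot show this.

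**Step 4. Other readings.** If the trend uses all scores, each participant's series contains both members of each pair and the change can be read off by eye. If baseline means the start of every session, both scores are summarised, and with complete pairs the mean change equals the difference between the two means. The median and IQR of the change cannot in general be recovered from separate summaries of start and end scores. Under neither reading does the plan specify the paired change.

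**The case against.** The strongest reply has four parts.

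- **The plan may use more than the post-session scores.** This stands in part. The trend sentence is not limited to post-session scores. A reader might infer that every pre-session score after session 1 is collected and never used. The documents do not support that, since it requires one reading of baseline and a further assumption about the trend.
- **Baseline is clear enough.** This largely stands. A reader might call SSQ baseline undefined, but Table 1 and Appendix Q together point to session 1. Naming it is a matter of clarity only.
- **Change is specified under S.A.2 because change is that aim.** This stands. S.A.1 concerns feasibility, usability and acceptability and sets hypothesis testing aside. The difference between the two paragraphs is not a contradiction.
- **There is other cover, and variation on arrival is not shown.** Both are true. The exit interview is assigned to S.A.1 and asks about symptoms that would deter reuse. Sessions stop for simulator sickness, and session duration is itself an outcome. A history of motion sickness, vertigo or dizziness excludes a survivor, which bears on some SSQ items. None of this gives symptom change session by session, and the exclusions do not reach fatigue, headache or difficulty concentrating.

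The reply does not identify any section that specifies a start-to-end change. That part of the point is unanswered.

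**Conclusion.** The point holds as an improvement to a descriptive analysis. The only measure labelled Acceptability is scheduled in start/end pairs, and the stated analysis leaves out the paired change, which is the summary that separates symptoms present on arrival from those arising during the session. Post-session scores, alone or against one session-1 score, cannot do so after session 1.

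The consequence is minor to moderate. No threshold or decision rule is tied to the SSQ, no error rate or sample size is affected, and the pairs can be tabulated from data already scheduled. The practical effect rests on two assumptions: that baseline is the session-1 pre-session score, and that arrival symptoms vary between sessions. The documents make both plausible but establish neither.

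A reader might infer that the planned summary will overstate headset sickness. The documents do not support a direction: arrival symptoms could be higher or lower than at session 1. Nor would the paired change isolate a headset effect. There is no control arm, exertion contributes, and at sessions 1 and 12 the arm assessments are also scheduled without a stated order relative to the SSQ.

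**What to change.** In the S.A.1 acceptability paragraph:

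1. Name the session-1 pre-session score as SSQ baseline.
2. Keep the planned post-session summary and add a descriptive end-minus-beginning change by session and participant (median, IQR), with the number of complete pairs at each session.
3. Show the pre-session scores by session, so that variation on arrival is visible.
4. Use the paired change in the per-participant trend.
5. Describe the change as session-related, not as an effect of the headset.

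No test is needed. The cost is a few lines of analysis text and some additional tabulation. No new form, visit or procedure is required.

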 - Stroke survivors will be excluded if they do not have score ranges that indicate mild to moderate severity on prior post-stroke neuropsychological tests, or the MoCA (15-25) using normative data based on education, age, and other standard demographic data, or other appropriate cognitive screening test selected by the speech language pathologist (also on this application) if the participant has aphasia, hemiopsia, other neurological or specific cognitive deficits, or demographic factors (e.g., education level) that prevents the participant from being accurately examined using MoCA or a modified MoCA; if cognition is within normal range then a FM (20-50), if they are unstable while standing unassisted, have a history of motion sickness/ vertigo/ dizziness/ seizures (a doctor's note will be requested for participants who do not believe their seizures will be triggered by the VR), claustrophobia, blind/deaf, and cannot hold the controller in their affected arm with or without the use of assistance.

Study Design/Methods

[figure not shown]

Figure 1: Study Schema

- Figure 1 depicts the overall study schema or flow as described below.

- Study Overview:
 - **S.A.1.** With the current drive for telerehabilitation and the advent of VR headsets, the examination of human factors perspectives is necessary before full implementation. End user perspectives regarding the impact, perceived usefulness, and perceived ease of use are essential, particularly in the older stroke population.
 - **S.A.2.** The rehabilitation team will measure changes on standardized measurements as part of standard of care.
 - **S.A.3.** Understanding the role of caregiver engagement upon stroke survivor rehabilitation outcomes and its potential impact on the quality of dyadic interpersonal relations is imperative for the sustainability of using VR for stroke rehabilitation in the home.
- Recruitment:
 - We will recruit 20 stroke survivor dyads (n=40) from the
 - Place: UT Physicians Department of Neurology Stroke Clinic, Brain and Behavioral Health Clinic, TIRR, Memorial Hermann, and Stroke Survivor Support Groups. In 2021, the clinic treated approximately 1000 stroke patients. Based on our knowledge of the clinic and previous experiences with stroke trial enrollment, enrolling 20 dyads over a 6-month recruitment period will be feasible. All rehabilitation sessions will take place in the Aging in Place (AIP) apartment.

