- The data will serve as preliminary data for subsequent competitive, peer-reviewed extramural grant applications that address telerehabilitation in stroke survivors within the home and the role of their caregiver.
 - Specifically, the proposed project addresses priorities outlined by institutes (e.g., National Institute of Neurological Disorders and Stroke, National Institute of Aging and National Institute of Nursing Research) within the National Institutes of Health (NIH) by investigating innovative approaches to promote health and well-being in patients and their informal caregivers living within the confines of a chronic disease. Specifically, stroke survivor acceptability data and knowledge derived from commercially available VR headset technology are needed to demonstrate:
 - The technology is acceptable for at-home use in stroke populations
 - The technology is capable of effecting improvement in upper extremity motor movement and cognition in stroke survivors.
- We will use the data from the proposed project to determine and complete the needed modifications to the home rehabilitation program using the Oculus VR headset in the post-stroke population.
- The data from this study will be used to plan an RCT to test the effectiveness of the intervention on improving upper extremity functionality and cognitive outcomes that can lead to improved independence during activities of daily living.
- We also plan to examine the role of the caregiver on home rehabilitation outcomes and the impact of caregiver participation during home rehabilitation sessions on stroke survivor-informal caregiver dyads and on caregiver burden.
- We anticipate submitting grant applications to the NIH and other appropriate foundations within 3 months from the time this project is completed.

References

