Appendix M
Therapy Follow Up Checklist

**Please answer the following questions regarding therapy visits
that have been received since the last study visit**

Occupational Therapy	YES/NO	# of sessions	Session Length
Therapy addressed:	 Home exercise program  Self-care (dressing, toileting, etc)  Household tasks (cooking, cleaning, etc)  Return to worktasks  Coordination  Community tasks (shopping, using public transportation, etc)  Cognition (memory, multi-tasking, attention, etc)	 Transfers  Casting/splinting  Vision  Sitting/standing balance  Arm/hand exercises - Number of repetitions: _____	
Physical Therapy	YES/NO	# of sessions	Session Length
Therapy addressed:	 Walking  Running  Vestibular exercises  Leg exercises - Number of repetitions: _____	 Rolling in bed  Standing balance  Transfers  Casting/bracing - Number of repetitions: _____	 Sitting balance  Home exercise program  Getting in/out of bed  Core exercises - Number of repetitions: _____
Speech Therapy	YES/NO	# of sessions	Session Length
Therapy addressed:	 Cognition (memory, multi-tasking, attention, etc)  Communication (speaking and/or understanding)  Swallowing		

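### The before-after Cohen's d is labelled a preliminary measure of Oculus VR effectiveness, but one group without a comparator cannot separate VR from home exercises, cues, outside therapy and retesting

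*Combined protocol and SAP*

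**What the plan says.** **The claim.** S.A.2 compares MoCA, Fugl-Meyer (FM) and ARAT at baseline and last session; Table 1 lists all three as primary outcomes. After the distribution is inspected, "either the paired t-test or the nonparametric Wilcoxon signed rank test will be used to evaluate the significance of the difference score". The summary measure is then given: "The effect size provided by Cohen's d measure, i.e., the standardized difference of mean score", and this "will provide a preliminary measure of the effectiveness of Oculus VR in this pilot study". The Intervention section adds that the study "will generate an estimate of the effect that can be used to inform the development" of RCTs. The text on future grant applications, just before the References, lists two things the data are needed to show, one being: "The technology is capable of effecting improvement in upper extremity motor movement and cognition in stroke survivors".

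**What participants receive besides VR.** Under Intervention, the therapist or research assistant (RA) helps the participant plan for "performing home exercises that will be provided to the participant at the first session". Appendix E has a block of cues for arm and hand exercise at home. Caregivers are encouraged to use the Appendix D cues during sessions. Appendix M asks about occupational, physical and speech therapy visits "that have been received since the last study visit"; Table 1 and Appendix Q schedule it from session 2 to the last session.

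**The hedges.** General Information words S.A.2 neutrally, as a calculation of change. S.A.2 calls the measure preliminary and gives formal inference second place. The Outcomes section leaves it to later RCTs to settle effectiveness.

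**The concern.** A before-after change in one group contains everything that happened to the participants over about four weeks, together with artefacts of measuring them twice. Calling its standardized size a measure of what Oculus VR does gives the design a property it lacks. Outside therapy was thought important enough to record at every visit from session 2 and to list as a secondary outcome, yet no step in S.A.2 uses it.

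At stake is the interpretation of three outcomes listed as primary, and of the figure handed to RCT planning. A reader of the results would take d as a VR effect when it describes the whole programme.

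**Working it through.** The plan states no assumed effect, SD, alpha or power, so there is no figure to reproduce. The check is mainly a reading of the text.

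**Step 1. What enters the change score.**

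| Source | Where | Outcomes mainly affected | Used in S.A.2? |
|---|---|---|---|
| VR sessions | Intervention; Appendix Q | FM, ARAT, MoCA | Yes, as the named cause |
| Home exercises from session 1 | Intervention; Appendix E | FM, ARAT | No |
| Caregiver and therapist cues | Intervention; Appendices D, E | All three | No |
| Outside therapy (not an exclusion) | Exclusion Criteria; Appendix M | All three: the form covers arm/hand exercise and cognition | No |
| Repeat testing | Table 1 | All three | No |
| Entry on a MoCA of 15-25 | Exclusion Criteria; Appendix Q | MoCA, by regression to the mean | No |

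On the last row, Appendix Q has the MoCA done before the first visit and repeated at session 1 only if it was missed then. The score that admits a participant can therefore also be the baseline score. This does not apply to those admitted on other tests.

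**Step 2. Why the VR share cannot be recovered.** Write the observed standardized change as d_obs = d_VR + d_other. The study estimates d_obs only: one equation, two unknowns. No group has d_VR = 0. More participants would estimate the same sum more tightly and would not split it.

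**Step 3. Illustration (assumed values, not the plan's).** Take d_obs = 0.5 and let s be the share from other sources, so d_VR = 0.5 × (1 − s):

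- s = 0: 0.50
- s = 0.25: 0.375
- s = 0.50: 0.25
- s = 0.75: 0.125
- s = 1: 0

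The design cannot tell these cases apart.

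Now let d_VR = 0. With n = 20, two-sided alpha 0.05 (assumed) and 19 degrees of freedom, the noncentrality is d_other × √20 = d_other × 4.472. The chance of p<0.05 on the paired t-test is then:

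- d_other = 0.2 (noncentrality 0.894): 0.136
- d_other = 0.3 (noncentrality 1.342): 0.247
- d_other = 0.5 (noncentrality 2.236): 0.565

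**Step 4. Do the hedges cover this?** Preliminary describes how firm the figure is. Ranking inference second describes how much weight the p-value gets. Leaving effectiveness to RCTs says who will settle the question. None says that the change may come from something other than VR, and the Intervention section carries the estimate forward to those RCTs.

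**The case against.** The best defence is that this is a feasibility pilot which does not claim to establish effectiveness. Its aim is worded as change, and it defers the question to RCTs. That stands as to tone, and it limits the severity. It does not answer attribution, because the sentence in S.A.2 still names Oculus VR as what d measures.

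It is also fair that the line on the technology's capability sits among grant priorities and lists what data are needed to show. It is not an analysis claim. It needs aligning, no more.

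Appendix M does contain a home-exercise-program box and a repetition count for arm/hand exercise. Both sit under therapy visits, so they describe what those visits covered. I found no record of adherence to the study's own home exercises in the sections available to me.

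Three stronger readings are tempting, and the documents do not support them:

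- **That the home programme outweighs VR.** A reader might multiply out the Appendix N sheets and set the result against the four-hour VR minimum. But the text on first-session exercises names no appendix. The main text cites Appendix N only for people who cannot complete the study. The therapist selects from it, the number selected is not given, and the list as reproduced may be incomplete. Appendix Q also lists twelve one-hour sessions, well above the minimum.
- **That Intervention and Potential Problems contradict each other on home exercises.** Exercises can be given at session 1 and also offered to those who leave. At most, it is unclear whether they are the same set.
- **That an RCT will be sized on d.** The text speaks of informing and planning RCTs. It does not say that d will set a sample size.

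**Conclusion.** The point holds as a fault of labelling and attribution. S.A.2 and the Intervention section assign to VR a change that the design can assign only to the four-week programme as a whole, plus retesting and possible regression to the mean. The size of the misattribution cannot be estimated; the VR share could lie anywhere from none to all. That range states what is not identified and is not a likely value. The Step 3 figures rest on assumed effects, an additive split and a 5% two-sided test, and they only show scale.

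The width of a confidence interval for d at n = 20 is a separate matter of precision and is not part of this point. Rival explanations differ by outcome: home exercise bears mainly on FM and ARAT, while outside cognitive therapy, retesting and entry selection bear on MoCA. The feasibility, usability and acceptability analyses are untouched. The sponsor should correct this before results are written up.

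**What to change.** 1. In S.A.2, replace the effectiveness sentence with: *standardized within-participant change over the 4-week programme (VR, home exercises, cues and any outside therapy); not an estimate of the effect of VR*. Align the effect-estimate wording under Intervention and the capability line in the grant text.
2. For RCT planning, carry forward the SDs, the pre-post correlation and completeness of measurement. Do not use d alone as the VR effect.
3. Tabulate the Appendix M therapy sessions and their length beside each participant's change in MoCA, FM and ARAT, descriptively. A summary in those with no outside therapy is optional; that group may be small, and the summary would not remove home exercise.
4. If enrolment is still open, add one question on home exercise to the Appendix M checklist. This version is dated 03/06/2024, after the stated November 2022 to October 2023 duration, so it may be too late; if so, state the gap as a limitation.
5. Clarify whether the first-session exercises are those in Appendix N.

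A control arm is not requested. Splitting the 20 as 10 v 10 would give power of about Φ(0.5 × √(10/2) − 1.96) = Φ(−0.84) = 0.20 at an assumed d of 0.5 and two-sided 0.05.

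The cost is SAP wording, one table and at most one checklist question. The downside is a weaker claim.
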